4.3 Completer Analysis Set

The Completer Analysis Set (CAS) will comprise all patients who were randomized, underwent and completed their assigned procedure, and who completed all post-procedure follow-up

visits (e.g. have at least the primary efficacy measures at post-procedure time points of weeks 1 and 2, and months 1, 3, 6, and 12). Analysis of the treatment effectiveness using CAS will be considered as sensitivity analysis to that performed using the FAS. However, if the efficacy outcome measures are missing completely at random (MCAR) or missing at random (MAR), then estimates of the treatment effect will be unbiased, and should produce results similar to those obtained using the FAS data with multiple imputation (MI) for the missing outcome measures.⁴

5.0 Statistical Analyses of Outcome Measures

5.1 General Exploratory Analyses

All statistical analyses will be performed using SAS® for Windows, version 9.4 or later. As a first step, descriptive statistics will be performed, and the normality of continuous variables evaluated using the Shapiro-Wilk test and through exploratory plots (e.g. histograms and Q-Q plots). Non-normal variables will be transformed to normality, using appropriate data transformations, or will be analyzed using non-parametric statistical methods. Frequency distributions, tabulations, and bar charts will be created to quantify categorical and binary variables. These exploratory analyses will help us assess data distributions, and also help identify any unusual, outlying or suspect observations.

Next, initial confirmatory analyses will be used to determine whether there are significant differences in baseline demographic and clinical variables between treatment arms, as well as between any comparable outside groups. These confirmatory analyses will include t-tests for continuous variables deemed to be normally distributed, or the non-parametric Wilcoxon Rank Sum test for non-normally distributed continuous variables. Binary and categorical variables will be analyzed using the Chi-Square goodness-of-fit test, or the Fisher's Exact Test, appropriate for categorical variables with small cell sizes. A lack of differences between treatment arms will be considered as evidence of adequate randomization; however, we expect that some baseline covariates will be imbalanced by treatment arm, given the small size of this study, due to chance.

5.2 Main Statistical Hypothesis

The null and alternative hypotheses for the primary efficacy outcome is given as:

Where Δ_{wt} is the change in weight (kg) at 12-months post-procedure minus baseline weight. In this trial, the null hypothesis will be rejected with type 1 alpha = 0.20.

5.3 Analysis of the Primary Efficacy Measure

The primary efficacy outcome for the proposed trial is total weight loss from baseline weight at 12-months post-randomization. Differences in the weight loss from baseline between the treatment arms will be compared using the two-sample t-test. In addition, we will also consider an ANCOVA model that looks at the group difference in mean weight loss from baseline, adjusting for baseline covariates that might be imbalanced by treatment arm. We will use the Wilcoxon Rank Sum test to compare the two treatment arms if the data are found to be non-normal as determined by exploratory plots.

[1]

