8.2.15 Randomization

Data documenting demographic information, medical history, physical examination, medication and prior treatment, clinical labs, pregnancy test, and urinalysis will be reviewed against the eligibility criteria to determine eligibility. The determination will be recorded on the relevant eCRF.

If a patient is determined to be eligible to participate in the study, the patient will be randomized.

Randomization will be determined using assignment by a computer-generated randomization scheme. Upon randomization/enrolment, each patient will be assigned a unique numeric patient identity code.

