3.2 Randomization

If all eligibility criteria for the study have been met by a given patient, and the patient consents to participate in the study, then this patient will be randomized into one of the two treatment groups via a computer-generated randomization scheme. Additionally, stratified randomization by diabetic status will be utilized to remove its potential confounding effect in comparing weight loss between treatment arms. Upon randomization/enrollment, each patient will be assigned a unique numeric patient identity code. Once randomized, the patient will be scheduled for their assigned procedure, and will follow the steps of the procedure as outlined in the clinical protocol.

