6.0 Missing Data

The clinical investigation team will make substantial efforts to ensure complete collection of data for all patients, and to accrue minimal loss to follow-up to optimize evaluation of the primary efficacy outcome. Our overall approach is to engage participants early on and keep them engaged through personal contact with the local center and access to information and resources that are relevant to them, their injury and their treatment. Furthermore, we do not expect the rates of missing data will be differential across treatment groups. As with most prospective studies, missing data will be unavoidable (even with excellent follow-up).

In order to impute the missing outcome data, analytic procedures will be utilized to ‘fill-in’ the missing body weights at 12 months’ post-procedure for those patients who do not have data on this primary endpoint. Specifically, a prediction model using completers (within each treatment group) will be created. In this case, a completer is a patient with data on body weight at 12 months’ post-procedure. The prediction model will include age, race, sex, and baseline body weight. We will then use multiple imputation to produce m random values for each missing 12 months’ post-procedure endpoint based on the prediction model. In this imputation process, the value of m will be set to 20, creating 20 “complete” data sets. Results of the two-sample t-test and rank test (and corresponding 95% confidence intervals) will be calculated over all 20 imputed

data sets based on the combination rules as specified by Rubin (1976, 1987)^{6,7}. Since only missing data at 12 months' post-procedure will be imputed, we assume that missingness is monotone.

Since the informative nature of missing data cannot be verified from the observed data, we will adopt a sensitivity analysis framework for reporting results. We will analyze data under a variety of modeling assumptions regarding how strongly the missingness mechanism is related to outcomes.⁵

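### Cheap improvement, not an error: randomisation is stratified by diabetic status, but the primary t-test uses neither that stratum nor baseline weight, and the additional ANCOVA would rarely pick the stratum up

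*SAP*

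**What the plan says.** - **Randomisation.** SAP 3.2 states that "stratified randomization by diabetic status will be utilized to remove its potential confounding effect in comparing weight loss between treatment arms". Protocol 8.2.15 says only "Randomization will be determined using assignment by a computer-generated randomization scheme", and Protocol 6.3 gives 27 per arm without naming a stratum. In the Protocol's statistical section, diabetic status appears only as a subgroup exploration (9.4.7).
- **Primary test.** SAP 5.3: "Differences in the weight loss from baseline between the treatment arms will be compared using the two-sample t-test". Protocol 9.4.2 has the same sentence.
- **ANCOVA.** Both sections will also consider an ANCOVA "adjusting for baseline covariates that might be imbalanced by treatment arm". Neither lists covariates or defines imbalance.
- **Non-normality.** SAP 5.3 moves to the Wilcoxon test "if the data are found to be non-normal as determined by exploratory plots". SAP 5.1 and Protocol 9.4.1 share a general rule: "Non-normal variables will be transformed to normality, using appropriate data transformations, or will be analyzed using non-parametric statistical methods".
- **Imputation.** SAP 6.0: "The prediction model will include age, race, sex, and baseline body weight". Diabetic status is not in that model. "Results of the two-sample t-test and rank test (and corresponding 95% confidence intervals) will be calculated over all 20 imputed" data sets; the ANCOVA is not mentioned there.

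**The concern.** The plan treats diabetic status as important enough to stratify on, then leaves it out of the analysis that decides the trial. Baseline weight enters only through the change score and the imputation model, not as a covariate. The ANCOVA does not close the gap: it is an addition, and its selection rule looks for imbalance, which stratification is designed to prevent in this very variable.

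What is at stake is efficiency and an error rate close to nominal, not bias. When the arms are balanced on a prognostic stratum, an unadjusted test still counts the between-stratum variation as noise, so its standard error is somewhat too large. Leaving out a prognostic baseline weight costs precision. Choosing covariates after seeing the baseline table also leaves the adjusted estimate less than fully pre-specified.

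**Working it through.** **1. The plan's own figure.** From SAP 3.8: mean losses of 8 and 3.3 kg, so the difference is 8 - 3.3 = 4.7 kg; SD 7 kg; two-sided alpha 0.20; 20% dropout. With n = 21 per arm, df = 40, the critical t is 1.303 and the noncentrality is 4.7 / (7 × √(2/21)) = 2.176. The noncentral t gives power of 80.9% (79.4% at n = 20). Then 21 / 0.8 = 26.25, rounded up to 27. The stated 21 and 27 reproduce.

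**2. Effect of ignoring the stratum on type I error.** Assume 30% diabetic, a stratum effect of g kg and total SD 7. The between-stratum variance is g² × 0.3 × 0.7. With the stratum balanced, the t-test's standard error is too large by the factor √(49 / (49 - g² × 0.21)). The approximate error rate is 2 × (1 - Φ(1.2816 × factor)).

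| g (kg) | Variance | Factor | Approximate type I error | Simulated (blocks of 2, 4, 6; with and without dropout) |
|---|---|---|---|---|
| 2 | 0.84 | 1.009 | 19.6% | 19.6–19.9% |
| 3 | 1.89 | 1.020 | 19.1% | 19.0–19.3% |
| 4 | 3.36 | 1.036 | 18.4% | 18.1–18.7% |

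The ANCOVA stays at 19.5–20.1%. With baseline weight as the only prognostic factor (correlation 0.4), the t-test stays at 19.7–20.1%.

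**3. Power on 21 completers per arm.** Simulation of 20,000 trials per setting: difference 4.7 kg, total SD 7, stratified blocks of 4 (assumed), 30% diabetic. The correlation is between baseline weight and weight change.

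| Assumed correlation; diabetes effect | t-test | ANCOVA | Change (points) |
|---|---|---|---|
| 0; 0 kg | 81.1% | 80.2% | -0.9 |
| 0.2; 2 kg | 80.9% | 81.6% | +0.7 |
| 0.3; 3 kg | 81.5% | 84.0% | +2.5 |
| 0.4; 4 kg | 81.8% | 87.4% | +5.6 |

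Over 15 to 45% diabetic the change runs from -0.9 to +5.7 points. Taken separately at 30% diabetic, baseline weight alone (0.2, 0.3, 0.4) gives +0.3, +1.9 and +4.2 points; diabetic status alone (2, 3, 4 kg) gives -0.7, -0.1 and +0.3. The power gain therefore comes mostly from baseline weight, and the stratum mainly restores the error rate.

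**4. Power inside the planned imputation.** 10,000 trials per setting: 54 randomised, 20% missing completely at random, m = 20, within-arm model on age, race, sex and baseline weight, same four scenarios.

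| Scenario | Planned t-test | ANCOVA, SAP imputation model | ANCOVA, diabetic status added to the model |
|---|---|---|---|
| 0; 0 kg | 76.5% | 75.9% | 74.8% |
| 0.2; 2 kg | 77.3% | 77.4% | 76.7% |
| 0.3; 3 kg | 77.0% | 78.9% | 78.2% |
| 0.4; 4 kg | 79.2% | 83.2% | 83.3% |

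The change is -0.6 to +4.0 points with the SAP's imputation model and -1.7 to +4.1 with diabetic status added. The median arm estimate stays at 4.66–4.75 kg throughout.

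**5. How often an imbalance rule would select diabetic status.** 40,000 trials, blocks of 2 to 8, 15 to 45% diabetic:

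| Rule | Stratified, all 54 | Stratified, after dropout | Unstratified |
|---|---|---|---|
| Chi-square p < 0.05 | at most 0.04% | at most 0.16% | 4.3–5.6% |
| Chi-square p < 0.2 | at most 1.4% | at most 4.1% | 19.8–21.9% |
| Standardised difference above 0.25 in size | at most 4.0% | 9–19% | 34–44% |

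**6. The Wilcoxon trigger.** With 21 per arm, moving a Shapiro-Wilk cut-off from 0.01 to 0.20 changes the verdict in 1.1–1.3% of trials (normal data) or 2.6–3.5% (skewness 1). Type I error stays at 19.7–20.2% and 20.6–21.1%.

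**The case against.** The strongest reply is that the plan already works. The t-test is unbiased, meets its stated power, and errs on the conservative side when the stratum matters. Stratification has already done the balancing that SAP 3.2 wants. The gain depends on prognostic strengths that no document gives. A 4 kg diabetes effect would exceed the whole expected sham loss of 3.3 kg, and Protocol 5.2 narrows the diabetic group by excluding HbA1c above 8% and current insulin or sulfonylurea use. Inside the imputation with diabetic status added, the ANCOVA loses power in two of the four scenarios. All of this stands. It limits the size of the point, but not the case for analysing as randomised with a covariate already collected.

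A reader might infer more, and the documents do not support it:

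- **That the t-test is invalid or the trial underpowered.** Steps 1 and 2 show otherwise.
- **That the plot-based Wilcoxon switch opens the error rate.** Taking the most favourable of t-test, Wilcoxon and ANCOVA would give a type I error of 24–28%. But SAP 5.3 sets an order for the first two and makes the ANCOVA an addition, and SAP 3.3 masks the analysts to arm identity. Step 6 shows that the switch itself matters little. Protocol 9.4.1 also allows non-parametric methods, so the Wilcoxon step does not conflict with the Protocol.
- **That Protocol and SAP contradict each other on randomisation.** A computer-generated scheme can be stratified, and SAP 1.0 gives the SAP precedence. The Protocol's silence is a documentation gap.

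**Conclusion.** The point holds as a low-cost improvement. The primary analysis does not reflect the stratified randomisation, and the ANCOVA's selection rule will rarely bring the stratum in. Diabetic status is selected in at most 4.1% of trials under the significance rules examined. A standardised-difference rule applied after dropout raises this to 9–19%, so rarely does not mean never.

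The t-test's type I error is about 18 to 19.9% instead of 20% for assumed stratum effects of 2 to 4 kg at 30% diabetic. Power changes by about -1 to +6 points on completers. Inside the imputation, a small loss is possible if the covariates are weakly prognostic. These figures rest on assumed correlations of 0 to 0.4, diabetes effects of 0 to 4 kg, 15 to 45% diabetic (30% for the error rates and the imputation runs), assumed block sizes and random dropout. Confidence in the size of the gain is therefore moderate. The Wilcoxon trigger and the missing Protocol line are not separate problems.

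**What to change.** - **SAP 5.3 and Protocol 9.4.2.** Make the primary analysis an ANCOVA of 12-month change in body weight on treatment arm, baseline weight and diabetic status, at two-sided alpha 0.20. Keep the unadjusted t-test and the Wilcoxon test as sensitivity analyses that do not replace it. Remove covariate selection by observed imbalance.
- **SAP 6.0.** Name this ANCOVA as the analysis pooled over the 20 imputed data sets.
- **Imputation model (optional).** Adding diabetic status makes the model compatible with the ANCOVA, but costs up to 1.1 points of power (75.9 to 74.8% in the null scenario) and does not move the arm estimate. The within-arm term is fragile if few participants are diabetic: some arm has at most one diabetic completer in 15.8% of trials at 15% diabetic, and in 0.2% at 30%. Any rule for sparse strata should be fixed in advance on masked data.
- **Protocol 6.3 and 8.2.15.** Add one line stating the stratification, in the same amendment.

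If the sponsor keeps the t-test as primary, the minimum is to list the ANCOVA covariates in advance and to say that the t-test decides and the Wilcoxon test is supportive.

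No new data are needed. SAP 1.0 calls for a protocol amendment when the primary analysis changes, and the Protocol's Statement of Compliance requires agreement from or notification of the funder and documented FDA and IRB approval. If neither covariate is prognostic, the statistical price is about 0.9 points of power on completers, and 0.6 to 1.7 points inside the imputation.

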5.4 Analysis of the Safety Measures

The primary safety endpoint will be the differences in adverse events at 12-months post procedure. The statistical analysis on the secondary outcome for safety will consider differences in the adverse events (AEs) at 30-days post-procedure.

5.5 Analysis of Secondary Efficacy Measures

Statistical assessments of the change in the continuous body-mass measures at 12-months from baseline (e.g. percent body-fat, excess weight loss) will follow the analyses described above for the primary efficacy measure. The binary outcome of > 5% weight loss will be statistically compared by treatment arm using the chi-square goodness-of-fit-test. Risk differences and relative risks, along with corresponding 95% confidence intervals, will be also calculated to quantify this group difference.

[How do we analyze the change in the multi-compartment composition?]

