9.4.3 ANALYSIS OF THE SECONDARY ENDPOINT(S)

Secondary outcomes include:

- 1) Change in body weight at timepoints other than 12 months
- 2) Percentage change in body weight
- 3) Achievement of a >5% reduction in body weight
- 4) Percentage of excess weight loss (EWL)
- 5) Change in multi-compartment body fat composition as measured by MRI

Differences by treatment arm in the proportion of participants with >5% weight loss will be statistically compared using the Chi-square goodness-of-fit-test. Risk differences and relative risks, along with corresponding 95% confidence intervals, will be calculated to quantify group differences in this endpoint.

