5.6 Analyses of Exploratory Measures

Several exploratory endpoints will be considered in the proposed trial as stated above, including blood pressure values, lipid profiles, serum obesity hormones, food intake, hunger assessments, QoL measures, and changes in taste perception. These endpoints will be quantified using a variety of assessment tools with both continuous and categorical scores. Statistical differences by treatment in these assessments will include the two-sample t-tests for continuous scores that are normally distributed, or the non-parametric Wilcoxon Rank Sum test for non-normally distributed continuous scores, while the binary and categorical scores will be analyzed using the Chi-Square goodness-of-fit test.

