5.9 Multiplicity

The primary analysis of efficacy is tested at the two-sided alpha level of 0.20. In addition, secondary analyses will consider the alpha = 0.20 two-sided type I error. Secondary analyses will be examined in the order specified, and will not be corrected for multiplicity of testing. For safety outcomes, multiplicity will not be considered since this study is not powered on safety.

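### Both documents name a chi-square goodness-of-fit test for between-arm comparisons of binary and categorical outcomes, including >5% weight loss; it is the wrong test for two randomised arms, and the 2x2 test probably meant should be named

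*SAP*

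**What the plan says.** For the >5% weight-loss endpoint, SAP 5.5 has the two groups "compared by treatment arm using the chi-square goodness-of-fit-test". Protocol 9.4.3 agrees: the proportions "will be statistically compared using the Chi-square goodness-of-fit-test". Both sections add two-sample effect measures; in the SAP these are "Risk differences and relative risks, along with corresponding 95% confidence intervals".

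The same test name appears in two other settings:

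- Baseline comparisons between arms, SAP 5.1 (matching protocol 9.4.1): "Binary and categorical variables will be analyzed using the Chi-Square goodness-of-fit test". Here Fisher's exact test is offered as the alternative, described as "appropriate for categorical variables with small cell sizes".
- Exploratory endpoints, SAP 5.6 (matching protocol 9.4.9): "binary and categorical scores will be analyzed using the Chi-Square goodness-of-fit test". No small-cell alternative is given, and SAP 5.5 and protocol 9.4.3 give none either.

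On the error rate, SAP 5.9 says that "secondary analyses will consider the alpha = 0.20 two-sided type I error", without correction for multiplicity. No section states an expected or reference proportion for any of these tests.

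**The concern.** A chi-square goodness-of-fit test asks whether one observed distribution matches proportions fixed in advance. Comparing two randomised arms is a different problem. Both proportions are estimated, both carry sampling error, and the appropriate test is one of independence (homogeneity) on the table of arm by outcome.

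As written, the named test cannot be run from the plan alone, because the analyst must first supply expected proportions that neither document gives. Different choices lead to different error rates, in opposite directions. SAP 1.0 describes its analyses as final and gives them precedence over the protocol, so the test for a listed secondary endpoint should not be left to interpretation. The missing small-cell rule in the efficacy and exploratory sections adds to this, since SAP 5.7 repeats the secondary analyses within gender, race and ethnicity groups in a trial of 54 randomised participants.

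**Working it through.** **Inputs from the documents** (SAP 3.8 and protocol 9.2, unless noted)

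- Mean loss at 12 months: 8 kg (BAE) and 3.3 kg (sham); common SD 7 kg; baseline weight 110 kg.
- 21 evaluable per arm, 27 randomised per arm, 20% drop-out; 1:1 allocation (SAP 3.1).
- Two-sided alpha of 0.20 for secondary endpoints (SAP 5.9).

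**The plan's own figure.** With a difference of 8 − 3.3 = 4.7 kg, the normal approximation gives 2 × [7 × (1.2816 + 0.8416) / 4.7]² = 20.0 per arm. The t distribution gives power of 0.794 at 20 per arm and 0.809 at 21, so 21 is the smallest adequate number. Then 21 / 0.8 = 26.25, rounded up to 27. The stated sample size reproduces.

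**Responder rates (assumption).** The documents give none. If weight change is normal and the threshold is 5% of 110 kg = 5.5 kg, the planning figures imply:

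- sham: 1 − Φ((5.5 − 3.3)/7) = 1 − Φ(0.314) = 0.377
- BAE: 1 − Φ((5.5 − 8)/7) = 1 − Φ(−0.357) = 0.640

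Type I error is shown for common rates of 0.30, 0.377 and 0.50.

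**Three statistics.** Let x and y be the responders in the BAE and sham arms, n the number per arm and m = x + y. Each statistic is compared with the 80th percentile of chi-square on 1 df, 1.2816² = 1.642.

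1. Pearson 2x2: (x/n − y/n)² / [p̄(1 − p̄)(2/n)], with p̄ = m/(2n).
2. Goodness of fit with the sham proportion q = y/n taken as known: (x − nq)² / [nq(1 − q)]. If q is 0 or 1, any difference is counted as a rejection.
3. Goodness of fit of responders to a 1:1 split between arms: (x − m/2)²/(m/2) + (y − m/2)²/(m/2) = (x − y)²/m.

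The exact type I error is the sum of the binomial probabilities of all pairs (x, y) for which the statistic reaches 1.642.

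| Per arm | Common rate | 1. Pearson 2x2 | 2. Sham taken as known | 3. 1:1 split |
|---|---|---|---|---|
| 21 | 0.30 | 0.215 | 0.402 | 0.130 |
| 21 | 0.377 | 0.195 | 0.426 | 0.114 |
| 21 | 0.50 | 0.171 | 0.441 | 0.070 |
| 27 | 0.30 | 0.199 | 0.363 | 0.134 |
| 27 | 0.377 | 0.208 | 0.346 | 0.105 |
| 27 | 0.50 | 0.220 | 0.342 | 0.072 |

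Over the wider range of rates from 0.1 to 0.7, the results are 0.171 to 0.226 (Pearson), 0.342 to 0.441 (sham taken as known) and 0.022 to 0.225 (1:1 split).

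**Why the two literal readings diverge**

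- Statistic 2 leaves out the sham arm's sampling variance, which is half of the total under 1:1 allocation. Its large-sample error is 2 × [1 − Φ(1.2816/√2)] = 0.365.
- Statistic 3 ignores the non-responders. In large samples it equals the Pearson statistic times (1 − p), where p is the common response rate, so its error is 2 × [1 − Φ(1.2816/√(1 − p))]: 0.126 at p = 0.30, 0.104 at 0.377 and 0.070 at 0.50.

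**Power** at rates 0.377 and 0.640: Pearson 0.640 and 1:1 split 0.445 at 21 per arm; 0.770 and 0.549 at 27 per arm. Power under statistic 2 is not comparable, because that test does not hold its level.

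**The case against.** The best defence is that this is only a misnomer. The text has the groups compared by arm, reports risk differences and relative risks, and at baseline pairs the test with Fisher's exact test, the usual small-cell alternative to a contingency-table chi-square. In the baseline comparisons neither arm is a natural fixed reference. The repeated name looks like text carried from protocol to SAP, and so does not show that anyone means to fix the sham proportion. An experienced analyst would run the 2x2 test, and its error rate is near nominal.

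Most of that stands. It makes the likely practical harm small, but it does not make the named test right, and it leaves a pre-specified analysis dependent on the analyst's reading.

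A reader might infer that the plan as named would roughly double the false-positive rate and give p-values that are too small. The documents do not support that. The 0.34 to 0.44 arises only if the observed sham proportion is taken as known, which no section says. The other literal reading is conservative at most response rates.

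**Conclusion.** The named test is wrong for these comparisons in all six sections and should be corrected. The probable intention was a 2x2 test, which would hold type I error at 0.17 to 0.22 against the nominal 0.20. Under a literal reading the error could lie anywhere from 0.07 to 0.44 at response rates of 0.30 to 0.50, depending on a choice that the plan does not state. This is therefore an ambiguity in specification, and no inflation of the error rate has been shown.

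The figures rest on assumed response rates and on 21 to 27 evaluable per arm; the power figures also need normality of weight change. They are for unstratified tests.

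A reader might also infer that the comparison with approved obesity treatments, which protocol section 3 gives as a reason for this endpoint, is compromised. It is not: response rates, risk differences and relative risks do not depend on the name of the test. The primary t-test and the sample size are likewise unaffected.

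**What to change.** - In SAP 5.1, 5.5 and 5.6 and protocol 9.4.1, 9.4.3 and 9.4.9, replace the goodness-of-fit name with the Pearson chi-square test of independence, and specify Fisher's exact test when any expected count is below 5. At 21 per arm that switch applies when the pooled rate is below 5/21 = 0.24 or above 0.76. Fisher's test is conservative here: at a rate of 0.377 its type I error is 0.115 (21 per arm) and 0.122 (27 per arm) at the nominal 0.20. The rule should therefore be fixed in advance.
- For the >5% endpoint, specify the Cochran-Mantel-Haenszel test stratified by diabetic status, the randomisation stratum in SAP 3.2. This goes beyond correcting the name, but it matches the design at no cost.
- Keep the planned risk difference and relative risk with their 95% confidence intervals.

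The cost is wording in two documents, with no extra data or participants. SAP 5.5 needs an edit in any case, because it still carries a bracketed drafting question about the body-composition analysis.
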